Appendix 2: Phase 1b Erdafitinib + Cetrelimab + Platinum Chemotherapy Cohort

CONFIDENTIAL – FOIA Exemptions Apply in U.S.

198

Appendix 2 Table 2: Pharmacokinetic, Immunogenicity, and Biomarker Samples for the Phase 1b Erdafitinib+ Cetrelimab + Platinum Chemotherapy Cohort (Up to and Including Amendment 4)

Assessments/ Procedure	Notes	Molecular Eligibility Screening Period	Full-Study Screening Period	Treatment Cycle 1			Treatment Cycle 2			Treatment Cycle 3	Treatment Cycle 4			All Other Cycles	End-of- Treatment ^a	Follow- up Period ^a
		≥28 days prior to C1D1	Within 28 days prior to C1D1	Day 1	Day 8 (±2)	Day 15 (±2)	Day 1 (±2)	Day 8 (±2)	Day 15 (±2)	Day 1 (±2)	Day 1 (±2)	Day 8 (±2)	Day 15 (±2)	Day 1 (±2)	Within 30 Days (+7) of last dose	Every 12 weeks
Note: These samples should be drawn on the day study drug is administered. ^b																
Erdafitinib PK ^c	Pre-dose erdafitinib ^e unless otherwise specified. See Section 9.3.			X	X	X	Pre-dose and 4h post- dose			X				C5D1, pre-dose and 4h post erdafitinib dose		
Erdafitinib Protein Binding Blood Sample	4 h Post-dose See Section 9.3.						X									
Cetrelimab PK ^c	Pre-infusion ^d and EOI ^f unless otherwise specified; See footnote h for detailed sampling timepoints for cycles after Cycle 3; not all samples are taken on Day 1. See Section 9.3.			X	X Any time dur- ing visit	X Any time dur-ing visit	X			X	X ^h	X ^h	X ^h	X ^h	X Any time during visit	At first follow-up visit, if possible
Cetrelimab Immunogenicity	Pre-infusion ^d See Section 9.3.			X		X	X			X	X			Pre- infusion for C5. Then every other cycle after C5	X Any time during visit	At first follow-up visit, if possible
Cisplatin PK ⁱ (Cohort DL2C+ DL2C1)				X			X			X	X					
Carboplatin PK ^j (Cohort DL2D + DL2D1)				X			X			X	X					
CCI [REDACTED]	Pre-dose erdafitinib ^d			X	X	X	X									

Appendix 2: Phase 1b Erdafitinib + Cetrelimab + Platinum Chemotherapy Cohort

CONFIDENTIAL – FOIA Exemptions Apply in U.S.

Assessments/ Procedure	Notes	Molecular Eligibility Screening Period	Full-Study Screening Period	Treatment Cycle 1			Treatment Cycle 2			Treatment Cycle 3	Treatment Cycle 4			All Other Cycles	End-of- Treatment ^a	Follow- up Period ^a
		≥28 days prior to C1D1	Within 28 days prior to C1D1	Day 1	Day 8 (±2)	Day 15 (±2)	Day 1 (±2)	Day 8 (±2)	Day 15 (±2)	Day 1 (±2)	Day 1 (±2)	Day 8 (±2)	Day 15 (±2)	Day 1 (±2)	Within 30 Days (+7) of last dose	Every 12 weeks
CCI [REDACTED]	Pre-dose erdafitinib ^d			X	X	X	X								Any time during visit	
CCI [REDACTED]	Pre-dose erdafitinib ^d			X			X			X				C5D1	Any time during visit	
Tumor tissue for PD-L1 testing and bladder cancer subtyping	Archival or fresh biopsy tissue must be available for biomarker analysis	X														
CCI [REDACTED] ^e			Optional				Optional								PD Optional	

Abbreviations: ctDNA= circulating tumor DNA; EOI=end of infusion; FGFR= fibroblast growth factor receptor; PD= progressive disease; PD-L1 = programmed cell death ligand 1; PK = pharmacokinetics; PBMC = peripheral blood mononuclear cells; TCR = T cell antigen receptor

^a The End-of-Treatment Visit will occur within 30 days after the subject discontinues treatment for any reason. This assessment should be done prior to the subject starting a new therapy. Follow-up visits will occur every 12 weeks (±7 days).

^b The sampling schedule may be adjusted based on PK analysis output generated during the study or other safety concerns.

^c If dose delay occurs, then samples should be collected on the actual day of drug administration, not on the originally scheduled administration day.

^d On Day 1 of Cycles 1 through 4, erdafitinib oral dose will be given before the start of cetrelimab infusion, followed by platinum (cisplatin or carboplatin) chemotherapy. Pre-dose PK sample for erdafitinib to be taken within 30 mins before Pre-infusion PK (cetrelimab and platinum-based [cisplatin or carboplatin] chemotherapy), and immunogenicity samples for cetrelimab collected within 30 mins before cetrelimab infusion begins.

^e Timepoint is relative to the dosing of erdafitinib. erdafitinib PK samples may be collected during the cetrelimab infusion if necessary; however, the sample should be drawn from the contralateral arm (opposite the cetrelimab infusion site).

^f As soon as possible after EOI.

^g Optional paired biopsies will be collected in the Phase 1b erdafitinib + cetrelimab + platinum-based chemotherapy cohort. An additional optional biopsy will be collected upon PD.

^h C4D1: Pre-infusion and EOI, C4D8: Post start of infusion, C4D15: Post start of infusion, and C5D1: Pre-infusion and EOI.

ⁱ For **Cisplatin**: PK samples are to be collected from the arm opposite from infusion site. If drug was administered via a central venous catheter, sample collection for PK should be from a different site.

Cisplatin PK sample to be drawn at C1D1: Pre-infusion, EOI (within 5 min), 2h (±10 min), 4h (±10 min), and 8h (±10 min); C2D1 and C3D1: Pre-infusion; C4D1: Pre-infusion, EOI (within 5 min), 1.5h (±10 min), 2h (±10 min), 4h (±10 min), 8h (±10 min); and at any unscheduled visit(s). Sampling times are relative to the beginning of the infusion. Pre-infusion samples should be drawn within 30 minutes before the infusion begins. Cisplatin is planned to be infused over 1 to 2h. If infusion duration is 1.75 to 2h, then the 2h PK sample can be eliminated as EOI would cover this 2h timepoint.

^j For **Carboplatin**: PK samples are to be collected from the arm opposite from infusion site. If drug was administered via a central venous catheter, sample collection for PK should be from a different site

Carboplatin PK sample to be drawn at C1D1: Pre-infusion, EOI (within 5 min), 1h (±10 minutes), 2h (±10 minutes), 4h (±10 minutes), and 8h (±10 minutes); C2D1 and C3D1: Pre-infusion; C4D1: Pre-infusion, EOI (within 5 min), 1h (±10 minutes), 2h (±10 minutes), 4h (±10 minutes), and 8h (±10 minutes); and at any unscheduled visit(s). Sampling times are relative to the beginning of the infusion. Pre-infusion samples should be drawn within 30 minutes before the infusion begins. Carboplatin is planned to be infused over 15 to 60 mins. If infusion duration is 45 to 60 min, then the 1h PK sample can be eliminated as EOI would cover this 1h timepoint.

Appendix 2: Phase 1b Erdafitinib + Cetrelimab + Platinum Chemotherapy Cohort

CONFIDENTIAL – FOIA Exemptions Apply in U.S.

200

1. INTRODUCTION

Refer to Section 1 of the protocol for the introduction. The introduction includes a description of urothelial bladder cancer, FGFR signaling, erdafitinib, PD-1/PD-L1 signaling, cetrelimab (summary of nonclinical data, summary of clinical data), platinum chemotherapy in metastatic urothelial cancer, overall rationale for the study, the anticipated benefits and risks for erdafitinib and cetrelimab, and the anticipated benefits and risks for platinum chemotherapy.

2. OBJECTIVES, ENDPOINTS, AND HYPOTHESIS

2.1. Objectives and Endpoints for Phase 1b (Dose Escalation)

Objectives	Endpoints
Primary	

 To characterize the safety and tolerability of erdafitinib in combination with cetrelimab and platinum (cisplatin or carboplatin) chemotherapy, and to identify the recommended Phase 2 dose(s) (RP2D) and schedule for erdafitinib with cetrelimab and platinum (cisplatin or carboplatin) chemotherapy 	
 Frequency and type of dose-limiting toxicity (DLT)
Secondary	

 To characterize the PK of erdafitinib in combination with cetrelimab, and platinum (cisplatin or carboplatin) chemotherapy 	
 Concentration and PK parameters of erdafitinib, cetrelimab, and platinum (cisplatin or carboplatin) chemotherapy

 To assess the immunogenicity of cetrelimab 	
 Detection of antibodies to cetrelimab and effects on serum cetrelimab levels
Exploratory	

 To assess the CCI To evaluate changes in CCI To assess changes in CCI To explore biomarkers (DNA, RNA, and/or protein) in tissue and blood samples that could CCI To explore the relationships between PK, PD, AE profiles, and CCI 	

2.2. Hypothesis for Phase 1b (Dose Escalation)

A RP2D(s) regimen of erdafitinib combined with cetrelimab and platinum (cisplatin or carboplatin) chemotherapy can be identified for safe treatment of subjects with metastatic or locally advanced urothelial cancer with select FGFR gene alterations.

3. STUDY DESIGN AND RATIONALE

3.1. Overview of Study Design

Refer to Section 3.1 of the main body of the protocol.

3.1.1. Phase 1b for Erdafitinib + Cetrelimab + Platinum (Cisplatin or Carboplatin) Chemotherapy Cohort

The Phase 1b erdafitinib + cetrelimab + platinum chemotherapy cohort represents the dose escalation part of the study. A Modified Toxicity Probability Interval method, mTPI-2, (Guo 2017) will be used by the Study Evaluation Team (SET, Section 3.4) to guide the dose escalation and RP2D(s) regimen recommendations (see Section 11.2, [Attachment 1](#) and the SET charter). The expected number of subjects to be treated in the Phase 1b erdafitinib + cetrelimab + platinum chemotherapy cohort is approximately 40. Three subjects (either wild-type or with select FGFR gene alterations) will be enrolled in the initial erdafitinib + cetrelimab + cisplatin dose level (50 mg/m²). If the starting dose is safe, 6 additional subjects will be enrolled into the escalated dose of cisplatin (60 mg/m²). Out of 6 subjects, up to 3 subjects can be wild-type and the other subjects should be with select FGFR gene alterations. Wild-type is defined as subjects without FGFR gene alteration and subjects with FGFR gene alterations other than the select FGFR alterations described in [Table 4](#). Approximately 10 additional subjects with select FGFR gene alterations will be enrolled at the MTD for erdafitinib + cetrelimab + cisplatin.

Three subjects (either wild-type or with select FGFR gene alterations) will be enrolled in the initial erdafitinib + cetrelimab + carboplatin dose level (AUC4 mg/mL/min). If the starting dose is safe, 6 additional subjects will be enrolled into the escalated dose of carboplatin (AUC5 mg/mL/min). Out of 6 subjects, up to 3 subjects can be wild-type and the other subjects should be with select FGFR gene alterations. Approximately 10 additional subjects with select FGFR gene alterations will be enrolled at the MTD for erdafitinib + cetrelimab + carboplatin.

An overview of dose levels of the Phase 1b erdafitinib + cetrelimab + platinum (cisplatin or carboplatin) chemotherapy cohort is described in [Figure 2](#). The dose levels within the platinum chemotherapy cohort are:

Erdafitinib + cetrelimab + cisplatin (DL2C or DL2C1)

Erdafitinib, cetrelimab and cisplatin start concurrently on C1D1. A maximum of 4 cycles of cisplatin will be administered. The DLT period is 2 cycles (6 weeks).

and

Erdafitinib + cetrelimab + carboplatin (DL2D or DL2D1)

Erdafitinib, cetrelimab and carboplatin start concurrently on C1D1. A maximum of 4 cycles of carboplatin will be administered. The DLT period is 2 cycles (6 weeks).

Refer to [Appendix 2 Table 4](#) for an overview of the Phase 1b: erdafitinib + cetrelimab + platinum chemotherapy dose levels.

Erdafitinib + cetrelimab + platinum (cisplatin or carboplatin) chemotherapy cohort:

The starting dose is 8 mg erdafitinib (no up-titration); 360 mg Q3W cetrelimab, and either 50 mg/m² Q3W for cisplatin (DL2C) or AUC 4mg/mL/min Q3W for carboplatin (DL2D).

If based on the rules below, dose escalation for cisplatin is DL2C to DL2C1.

If based on the rules below, dose escalation for carboplatin is DL2D to DL2D1.

The following rules for escalation apply for the Phase 1b erdafitinib + cetrelimab + platinum (cisplatin or carboplatin) chemotherapy cohort:

- At least 3 subjects may be dosed in each dose level that will be explored.
- A staggered enrollment strategy will be applied to the first 3 subjects in a dose level. A minimal interval of 24 hours between a subject's first dose will be required.
- At least 3 subjects per dose level are required to complete the DLT evaluation period or be discontinued for DLT before the SET can determine the dose and schedule for the next dose cohort.
- The SET will evaluate all available data including, but not limited to, PK, PD, safety, and preliminary anti-tumor activity, and will decide whether to escalate, stay at the current dose, or de-escalate the dose level based on the mTPI-2 guidelines outlined in [Attachment 1](#). These are briefly explained for the case with 3 subjects treated at a specific dose of platinum (cisplatin or carboplatin) chemotherapy:
 - If no subject at a specific dose level of platinum (cisplatin or carboplatin) chemotherapy experiences a DLT, dose escalation may proceed. as guided by mTPI-2. The SET will confirm the dose level chosen for the next dose cohort.
 - If 1 out of 3 subjects at a specific dose level of platinum (cisplatin or carboplatin) chemotherapy experiences DLT during the DLT evaluation period, then the SET may decide to enroll additional subjects before escalating the dose of platinum-based chemotherapy.
 - If 2 out of 3 subjects at a specific dose level of platinum (cisplatin or carboplatin) chemotherapy experience DLT during the DLT evaluation period. The SET will confirm the dose level chosen for the next dose level.
 - If 3 out of 3 subjects at a specific dose level of platinum (cisplatin or carboplatin) chemotherapy experience DLT during the DLT evaluation period. The SET will confirm the dose level chosen for the next dose cohort.
- Dose escalation guided by the SET may continue until the RP2D is identified.
- The identification of the RP2D will be based on the totality of data from all dose cohorts tested.
- The SET will determine whether to modify or terminate dose levels, include additional dose levels, change doses or schedules of either drug, modify the study conduct if deemed necessary, and select the RP2D regimen for Phase 2 based on the emerging data (see Section [3.4](#)).
- Intra-subject dose escalation is not allowed and subjects in Phase 1b erdafitinib + cetrelimab + platinum chemotherapy dose levels will not be entered into Phase 2.

3.2. Study Design and Starting Dose Rationale

Refer to Section 3.2 of the main body of the protocol.

3.2.1. Rationale for the Combination of Erdafitinib, Cetrelimab, and Platinum (Cisplatin or Carboplatin) Chemotherapy

3.3. Dose-Limiting Toxicity Evaluation and Determination of RP2D

During Phase 1b, subjects will initially be enrolled into the starting dose of cisplatin or carboplatin (DL2C and DL2D) based on the mTPI-2 method. (Guo 2017) After the last subject in each group (minimum of 3 DLT evaluable subjects) has completed the DLT observation period or developed a DLT, the SET will evaluate all available safety data and make the decision whether to escalate, stay at the current dose or de-escalate the dose of platinum chemotherapy with the second group of subjects treated, based on the guidelines outlined in and in the SET charter. Based on emerging clinical data, the SET might decide to adjust the dose of cisplatin and/or carboplatin or terminate individual dose levels if deemed necessary. No intra-subject dose escalations will be allowed throughout this study.

3.3.1. Definition of Dose-Limiting Toxicity for Phase 1b (Dose Escalation)

Toxicities will be graded for severity according to the NCI-CTCAE, version 5.0. Only toxicities that occur during the DLT evaluation period will be used to define DLTs and for dose escalation decisions, but toxicities that occur during the entire treatment period will be recorded and considered in decisions regarding the RP2D.

The DLT evaluation period for the Phase 1b erdafitinib + cetrelimab + platinum (cisplatin or carboplatin) chemotherapy cohort is defined as 2 full cycles (6 weeks) of erdafitinib, cetrelimab, and platinum chemotherapy from the start of the first erdafitinib dose.

If the subject receives more than 75% of any of the study drugs in the DLT evaluation period, the subject will be evaluable for DLT. If the subject received less than 75% of each assigned dose due to reasons other than toxicities (eg, disease progression, missed appointments, non-compliance, subject withdrawal), the subject may be replaced with a new subject. All available safety data from subjects will be taken into consideration by the SET. Dose-limiting toxicities are defined as any of the events listed in [Appendix 2 Table 3](#).

Appendix 2 Table 3: Dose-Limiting Toxicity Criteria for Phase 1b: Erdafitinib + Cetrelimab + Platinum Chemotherapy cohort

Criteria for Non-hematological Toxicity	
	Exceptions
• Any Grade 3	Asthenia, anorexia, fever, or constipation
	Fatigue that improves to Grade ≤ 2 in ≤ 7 days
	Nausea lasting for ≤ 7 days responding to BSC ^a
	Vomiting and diarrhea that resolves in ≤ 3 days with BSC ^a
	Laboratory abnormalities that do not require hospitalization and are not felt to be clinically significant by the investigator
	Tumor flare (defined as local pain, irritation, or rash localized at sites of known or suspected tumor) that improves to Grade ≤ 2 in ≤ 7 days
	Elevation in AST or ALT for <7 days
• Any Grade 4	None
• Any Grade 5	None
• Elevation in AST or ALT >3 x ULN meeting criteria for Hy's law ^b	
Criteria for Hematological Toxicity	
Neutrophil count decreased: Grade 4 for >7 days	
Febrile neutropenia: Grade ≥ 3 or 4	
Platelet count decreased: Grade 3 with clinically significant bleeding or Grade 4	
Any Grade 5 toxicity	

Abbreviations: ALT=alanine aminotransferase; AST=aspartate aminotransferase; BSC=best supportive care; ULN=upper limit of normal.

^a Best supportive care (including electrolyte and hormone supplementation where clinically applicable) according to institutional standards or as outlined in Section 8.1. Routine primary prophylaxis is not permitted for subjects who are under evaluation for DLTs; For the use of CSFs after the DLT period ends, utilize (NCCN/EORTC 2018) guidelines.

^b Concurrent elevation of bilirubin >2 times institutional ULN without initial evidence of cholestasis and no alternative etiology for AST/ALT elevation.

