Two new regimens will be explored where erdafitinib and cetrelimab will be combined with either cisplatin or carboplatin. In the Phase 1b erdafitinib + cetrelimab + platinum chemotherapy cohort, the doses of erdafitinib (8 mg daily, no up-titration) and cetrelimab (360 mg every 3 weeks [Q3W]) are constant, while doses of cisplatin and carboplatin may be adjusted based on dose-limiting toxicity as described in the protocol and within the range of acceptable doses in the prescribing information (US prescribing information, EU SmPC, or equivalent for the region/country).

Erdafitinib + cetrelimab + cisplatin (erdafitinib + cetrelimab + cis) cohort:

First line subjects with or without select FGFR alterations will receive erdafitinib and cetrelimab in combination with cisplatin. The starting dose level of cisplatin will be 50 mg/m² administered intravenously on Day 1 of a 3-week cycle (DL2C). If the mTPI-2 criteria for escalation are met in DL2C, the dose of cisplatin will be increased to 60 mg/m² (DL2C1). The DLT period for dosing level DL2C and DL2C1 will be 2 cycles (6 weeks/42 days).

Erdafitinib + cetrelimab + carboplatin (erdafitinib + cetrelimab + carbo) cohort:

First line subjects with or without select FGFR alterations will receive erdafitinib and cetrelimab in combination with carboplatin. The starting dose of carboplatin (AUC4 mg/mL/min) administered intravenously on Day 1 of a 3-week cycle (DL2D). If the mTPI-2 criteria for escalation are met in DL2D, the dose of carboplatin will increase to AUC5 mg/mL/min with a maximum dose of 750 mg (DL2D1). The DLT period for dosing level DL2D and DL2D1 will be 2 cycles (6 weeks/42 days).

Phase 2 (Dose Expansion): (APPENDIX 3: PHASE 2 ERDAFITINIB +/- -CETRELIIMAB)

Two dosing arms may be explored: Arm A and Arm B

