Appendix 2 Table 7 : Dose Modifications for Cisplatin and Carboplatin

Category	Cisplatin		Carboplatin	
Starting dose	50 mg/m ²	60 mg/m ²	AUC 4 mg/mL/min (maximum dose 600 mg)	AUC 5 mg/mL/min (maximum dose 750 mg)
1st dose modification	Stop cisplatin but continue erdafitinib+ cetrelimab	50 mg/m ²	Stop carboplatin but continue erdafitinib+ cetrelimab	AUC 4.5 mg/mL/min (maximum dose 675 mg)
2nd dose modification	N/A	Stop cisplatin but continue erdafitinib+ cetrelimab	N/A	Stop carboplatin but continue erdafitinib+ cetrelimab

Creatinine clearance (CrCl)

CrCl will be based on the original weight-based Cockcroft and Gault formula ([Attachment 8](#)). The subject's CrCl at Screening must be ≥ 30 mL/min to receive carboplatin and ≥ 60 mL/min to receive cisplatin prior to each cycle of platinum chemotherapy. Cisplatin may be delayed for up to 21 days (1 cycle) to allow the subject time to recover from the toxicity. If a subject's CrCl value has not returned to ≥ 30 mL/min within 42 days (2 cycles) after the previous dose, cisplatin must be discontinued.

In general, study drug(s) should be held for AEs \geq Grade 3 that are not attributable to erdafitinib, cetrelimab, platinum chemotherapy, or the disease under study. If the event resolves to Grade 1 or baseline within 4 weeks, platinum chemotherapy and erdafitinib may be reintroduced at one dose level lower. If the same toxicity does not recur or worsen within 4 weeks after re-starting therapy, then cetrelimab may be reintroduced at the same dose. Following re-introduction of study drugs, if the same AE recurs at \geq Grade 3 or there is a second incidence of a \geq Grade 3 event that is not attributable to erdafitinib, cetrelimab, platinum chemotherapy, or the disease under study, study drugs should be permanently discontinued.

For toxicity associated with platinum chemotherapy, the AE must resolve to Grade ≤ 1 or baseline prior to starting subsequent cycle. For individual subjects requiring a dose modification, treatment

for each new cycle may be delayed if the scheduled off-drug periods are not adequate to allow for recovery to Grade ≤ 1 or the baseline status of the subject.

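### The platinum-cohort DLT period is both two full cycles and 42 days; these part when cycle 2 is delayed, so a subject with one platinum dose can count as DLT-free

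*Protocol*

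**What the plan says.** **Length of the period.** Appendix 2 Section 3.3.1 states that the DLT evaluation period "is defined as 2 full cycles (6 weeks) of erdafitinib, cetrelimab, and platinum chemotherapy from the start of the first erdafitinib dose". The Synopsis puts it in days for the cisplatin levels, "The DLT period for dosing level DL2C and DL2C1 will be 2 cycles (6 weeks/42 days", and does the same for the carboplatin levels.

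**Delay of cycle 2.** All of this is in Appendix 2 Section 6.4.4.
- Recovery comes first: "For toxicity associated with platinum chemotherapy, the AE must resolve to Grade" 1 or lower, or to baseline, before the next cycle starts.
- For subjects who need a dose modification, treatment "for each new cycle may be delayed if the scheduled off-drug periods are not adequate to allow for recovery". No maximum is given.
- Under the creatinine-clearance heading, "Cisplatin may be delayed for up to 21 days (1 cycle) to allow the subject time to recover from the toxicity". If clearance has not returned to the stated threshold "within 42 days (2 cycles) after the previous dose, cisplatin must be discontinued".

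**Who counts.** Under Appendix 2 Section 3.3.1, if a subject "receives more than 75% of any of the study drugs in the DLT evaluation period, the subject will be evaluable for DLT". Replacement is for subjects short on each assigned drug for reasons other than toxicity. Only toxicities inside the period define DLTs and feed escalation decisions.

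**When the decision is made.** Appendix 2 Sections 3.1.1 and 3.3 let the Study Evaluation Team (SET) decide once at least three subjects have completed the period or had a DLT. Neither section sets a condition on the second platinum dose. In Attachment 1, 0 DLTs among 3 subjects means escalate.

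**The concern.** The period is defined twice, once by exposure and once by the calendar. The protocol does not say which holds when cycle 2 slips. On the calendar reading, a late second dose gets a shortened observation time, or none.

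The loss is not random. A cycle is delayed because the subject had toxicity in cycle 1. The DLT criteria (Appendix 2 Table 3) do not list failure to start cycle 2 on time, and several events that can delay it are not DLTs: Grade 2 toxicity, Grade 4 neutropenia of 7 days or less, and Grade 3 platelets without clinically significant bleeding. The evaluability rule then keeps such a subject in the denominator, and the replacement rule does not take the subject out because the shortfall is due to toxicity.

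What is at stake is the DLT count that drives escalation of cisplatin or carboplatin, and the choice of the MTD at which about 10 further subjects per regimen are enrolled. There is a practical side too. Routine primary prophylaxis is barred while a subject is under DLT evaluation (Appendix 2 Section 6.4.3), so sites need to know whether a delayed cycle 2 is still inside the period.

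**Working it through.** **1. The plan's own figure.** The cycle is 21 days, so 2 × 21 = 42 days. This reproduces the Synopsis and holds when cycle 2 starts on day 22.

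**2. Effect of a delay if the calendar governs.** With C1D1 as day 1, the second dose falls on day 22 + d. Days observed from that dose to day 42, inclusive, are max(0, 21 − d).

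| Delay d (days) | Day of dose 2 | Days observed after dose 2 |
|---|---|---|
| 0 | 22 | 21 |
| 7 | 29 | 14 |
| 14 | 36 | 7 |
| 20 | 42 | 1 |
| 21 | 43 | 0 |

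At the 21-day cisplatin limit the second dose comes the day after the period closes. If the +2-day visit window is also used, a delay of 19 days is enough (22 + 19 + 2 = 43).

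**3. Does the evaluability rule remove such a subject?** Platinum received is 1 of 2 doses, or 50%. Erdafitinib is taken once daily, and 75% of 42 is 31.5, so 32 doses pass the threshold. Passing on any one drug is enough. If erdafitinib continues, as Section 6.4.4 permits when only platinum is modified, the subject is evaluable.

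**4. A subject with no second platinum dose.** Appendix 2 Table 5 calls for a first dose modification when platelets fall below 50 without bleeding. Table 7 makes the first modification at the starting levels (DL2C, DL2D) a stop of platinum. Table 3 counts a platelet decrease as a DLT only at Grade 3 with clinically significant bleeding or at Grade 4. A fall below 50 that is neither can therefore end platinum after one dose without a DLT, and the subject still passes step 3.

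**5. Attachment 1 check.** With p_T = 0.33, equivalence interval 0.28 to 0.38 and a Beta(1,1) prior (assumed), the rows for 0 to 6 DLTs at n = 3 to 9 reproduce as printed. For n = 3 they are E, S, D and DU for 0, 1, 2 and 3 DLTs.

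**6. Illustration of the bias.** The documents give neither a DLT rate nor a frequency of delay, so these inputs are assumptions. Let the true two-cycle DLT rate be 0.33 and let a share f of the cumulative hazard fall in cycle 1. The cycle-1 risk is p₁ = 1 − 0.67^f. If k of 3 subjects have no second dose inside the period, P(0 of 3) = 0.67^(3−k) × (1 − p₁)^k.

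| f | p₁ | k = 0 | k = 1 | k = 2 | k = 3 |
|---|---|---|---|---|---|
| 0.25 | 0.095 | 0.301 | 0.406 | 0.548 | 0.741 |
| 0.50 | 0.181 | 0.301 | 0.367 | 0.449 | 0.548 |
| 0.75 | 0.259 | 0.301 | 0.332 | 0.367 | 0.406 |

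The direction is the same throughout; the size depends heavily on f and k.

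**The case against.** A reader might infer that the period is fixed at 42 days whatever happens. The documents do not settle that. The definition leads with full cycles of all three drugs and puts the weeks in parentheses, so a subject without a second platinum cycle could be said not to have completed the period. Where the protocol wants a clock that ignores delays, as for disease assessments, it says so. Against that, the Synopsis gives days, the clock starts at the first erdafitinib dose, and the evaluability rule does not require platinum. What stands is that the protocol does not say which definition governs.

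A reader might also take 21 days as a general toxicity delay for both agents. The sentence concerns cisplatin and sits under the creatinine-clearance heading. The general delay sentence applies to subjects who need a dose modification, and at DL2C and DL2D the first modification is to stop platinum. Section 6.4.6 stops platinum for listed Grade 3 or 4 events that do not resolve within 7 days, and many severe events are DLTs already. This narrows the route to a late second dose. It does not close it, because the recovery requirement applies without any dose modification, and stopping platinum leaves the one-dose subject of step 4.

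There are also safeguards. The SET reviews all available safety data and confirms each step, toxicity over the whole treatment period informs the RP2D, at least 6 subjects are needed at the RP2D, and a cumulative review follows Cycle 2. The SET charter, which is not shown, may say more. These soften the consequence. None of those in the protocol corrects the DLT count entered in Attachment 1, and the post-Cycle 2 review is not made a condition of escalation.

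**Conclusion.** The point holds as an unresolved conflict between two definitions, made consequential by the evaluability rule. Following the text, a subject with one platinum dose can be entered as DLT-free, and this biases the DLT count downward.

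The size is unknown. The second dose falls wholly outside 42 days only at a delay of about 19 to 21 days; shorter delays cut the observation time in part. Under the assumptions in step 6, P(0 of 3) moves from 0.30 to 0.33–0.41 with one such subject and to 0.41–0.74 with all three. It would be tempting to quote one figure, such as 0.55 for three subjects, as the chance of wrongly escalating. The documents do not support that: it needs an equal split of hazard between cycles, all three subjects affected, and delayed subjects with the same underlying risk as the others.

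This should be corrected because it is cheap and bears on escalation. It does not show that any escalation decision was wrong.

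**What to change.** Reconcile the Synopsis with Appendix 2 Sections 3.3.1 and 6.4.4, and carry the result into the SET charter:

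1. State that the two-cycle definition governs when cycle 2 slips. DLT observation then runs to the end of the subject's actual second platinum cycle, and the subject is not entered in Attachment 1 as DLT-free before that. At a 21-day delay the period is 42 + 21 = 63 days.
2. Bring the evaluability wording, which accepts any one of the study drugs, into line with a period defined by two cycles that include platinum.
3. State how a subject who never receives a second platinum dose is counted, since item 1 gives that subject no end point.

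No dose, delay or discontinuation rule changes. The cost is a few sentences and a SET decision up to about 3 weeks later when cycle 2 is delayed. Because the bar on routine primary prophylaxis is tied to the DLT period, the sponsor should also say how that passage reads when observation runs longer.
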